## List of abbreviations

ADL	Activities of daily living
ADR	Adverse drug reaction
AE	Adverse event
APD	Advanced Parkinson's disease
AUDD	Authorization for use/Disclosure of data
BMQ	Beliefs Medication Questionnaire
CSAI	Continuous subcutaneous apomorphine infusion
DBS	Deep brain stimulation
eDRF	Electronic data recording form
FAS	Full analysis set
FOG	Freezing of gait
HCRU	Healthcare Resource Utilization
ICD	Impulsive compulsive disorder
ICF	Informed consent form
LAR	Legal authorized representative
LCIG	Levodopa-carbidopa intestinal gel
LEDD	Levodopa equivalent daily dose
MedDRA	Medical dictionary for regulatory activities
MMSE	Mini-Mental State Examination
NMSS	Non-Motor Symptoms Scale for Parkinson's Disease
PD	Parkinson's disease
PDQ-8	Parkinson's Disease Quality of Life Questionnaire
PDSS-2	Parkinson's Disease Sleep Scale-2
PEG-J	Percutaneous endoscopic gastrostomy- with jejunal extension
PMOS	Post Marketing Observational Study
PRO	Patient reported outcome
QC	Quality control
QUIP-RS	Questionnaire for Impulsive-Compulsive Disorders in Parkinson's Disease - Rating Scale
SAE	Serious adverse event
SAP	Statistical analysis plan
SAS®	Statistical analysis system
SD	Standard deviation
UPDRS	Unified Parkinson's Disease Rating Scale

## 1 Study protocol and scope

This statistical analysis plan (SAP) describes the final analysis of "COSMOS". It is based on the final version of the protocol (no. P16-831), dated 14 June 2017, and on Administrative change no. 1, dated 02 November 2017.

## 2 General definitions and procedures

#### 2.1 Software

Data entry is performed by means of the electronic data recording form (eDRF) system secuTrial®. Statistical analyses will be carried out with the SAS® package (version 9.4).

#### 2.2 Coding

Coding will be performed by the medical advisor. The codes will be added to the exported study database in SAS.

MedDRA (English version) will be used for coding of medical history, adverse events and product complains.

For the coding system the latest available version at the time of coding start will be used. PD (Parkinson's disease) medication and concomitant medication (for indications secondary to PD) will not be coded.

#### 2.3 Procedures prior to statistical analysis

After completion of check of all available study data, the database will be closed. Data Management ensures that no data modifications are possible by Biostatistics within this database. Thereafter, only the responsible data manager and the project statistician will be privileged to have access to the database. Any changes to the analyses after the SAP has been finalized will be clearly described in the study report.

After database closure the data will be transferred electronically to the statistical software package SAS® data set format for statistical analysis. The SAS® data sets will be considered as source data sets for statistical analysis.

#### 2.4 Reporting standard

A report for this analysis will be generated based on AbbVie standards. The report format is based on PMOS Study Results Report (Template\_[study\_]-pmos-results-rpt.docx) using relevant sections of the respective PMOS Study Result Report - Preparation Guide, version 03, June 2017. Sections that are not relevant to an epidemiological study will be removed.

#### 2.5 Quality control

The SAP is consistent with the underlying study protocol. If there is a need for deviating substantially from the protocol-defined analysis, this is described in detail. The methods described in this SAP are mandatory for statistical programming.

Quality control (QC) of statistical programming will be performed according to the QC plan, which specifies all planned actions to ensure that the performed analyses are correct, traceable and in line with the planned analysis as specified in the SAP. The QC plan also includes filing of statistical programs, outputs and documentation of QC. It is finalized by the project statistical programmer before the start of any programming activities.

Documentation of QC is filed in the trial master file.

## 3 Study objectives

The study objectives are the following:

## 3.1 Primary objective

The primary objective of the study is to evaluate the percentages of Advanced PD patients on levodopa-carbidopa intestinal gel (LCIG) monotherapy right after LCIG initiation and at 3, 6, 9, and 12 months, respectively.

## 3.2 Secondary objectives

The secondary objectives of this study are:

- To describe PD medication management, and the main reasons justifying their use, directly prior to LCIG initiation, at LCIG initiation and during long-term LCIG treatment
- To describe LCIG infusion settings and substantial dose adjustments and the respective reasons
- To describe the Healthcare Resource Utilization (HCRU)
- To identify the physician's and patient's/caregiver's overall preference for the pharmacological treatment approach using LCIG as monotherapy vs. LCIG plus add-on PD medication
- To identify predictors for achieving long-term monotherapy with LCIG vs. LCIG plus add-on PD medication, based on the patient's profile and the physician's profile
- To describe the latency from LCIG initiation until LCIG is given as a monotherapy and the average duration of LCIG monotherapy
- To describe the latency from the initiation of LCIG therapy until the introduction or tapering of each PD medication, or until substantial dose adjustments of LCIG
- To evaluate the percentage of patients who are on LCIG monotherapy, PD medication management and HCRU for the participating countries who have enrolled a minimum of 20 study subjects

## 4 Essential features of the study design

## 4.1 Type of study

This is a multi-country, retrospective and cross-sectional, post-marketing observational study (PMOS) of patients with APD (advanced Parkinson's disease) treated with LCIG in a routine clinical setting. It was planned to be conducted in approximately 15 countries.

#### 4.2 Study population

Approximately 400 patients were to be included in the study. The study population consists of adult patients diagnosed with APD, on current treatment with LCIG, and treated with LCIG for at least 12 months prior to study inclusion.

The participating sites were to be hospitals or clinics experienced in treating patients with APD, and with experience in LCIG treatment. Participating physicians should have been involved in the respective patient's management since initiation of LCIG therapy. All eligible patients at a given site were to be enrolled consecutively in order to minimize selection bias.

#### 4.2.1 Inclusion criteria

Patients were eligible for study participation if all of the following criteria were fulfilled:

- 1. Patients diagnosed with APD and on LCIG treatment for at least 12 months
- 2. Patient must have been on continuous LCIG treatment for at least 80% of days in the preceding year
- 3. Patients must be treated by the same physician (PI or co-investigator) since the initiation of LCIG treatment
- 4. Decision to treat with LCIG was made and therapy was started by the physician prior to any decision to approach the patient to participate in this study
- 5. Prior to any data collection, the patient, or legal authorized representative (LAR) has voluntarily signed an Authorization for Use/Disclosure of Data (AUDD)/informed consent form (ICF) according to national regulations after the study has been explained and the subject has had the opportunity to have questions answered

#### 4.2.2 Exclusion criteria

[figure not shown]
Patients with the following criteria were not eligible for study participation:

- 1. Participation in a concurrent or a previous interventional clinical trial during which the patient was on LCIG therapy
- 2. Lack of motivation or insufficient language skills to complete the study questionnaires

#### 4.3 Study schedule

This study consists of one single visit. The observational period is mainly retrospective and includes one cross-sectional study visit. Data gathered were derived from the time prior to initiation of LCIG therapy until the day of the study visit (see Figure 4-1). Patients were enrolled starting from 14 December 2017.

Figure 4-1: Study schematic

#### 4.4 Methods of measurement and documentation

Patient data and site characteristics were to be documented on the eDRF. In addition, patients were asked to complete the following questionnaires: Parkinson's Disease Quality of Life Questionnaire (PDQ-8), Questionnaire for Impulsive-Compulsive Disorders in Parkinson's Disease - Rating Scale (QUIP-RS), Parkinson's Disease Sleep Scale-2 (PDSS-2), and Beliefs Medication Questionnaire (18-item BMQ). Physicians should complete the following questionnaires: Unified Parkinson's Disease Rating Scale (UPDRS), Non-Motor Symptoms Scale for Parkinson's Disease (NMSS), Mini-Mental State Examination (MMSE), and Healthcare Resource Utilization Questions (HCRU). Data from questionnaires were also to be recorded on the eDRF.

An overview of activities and procedures is given in Table 4-1.

Table 4-1: Activities and procedures

Activity/Procedure	Before LCIG initiation	LCIG initiation	During LCIG treatment	Patient visit
	Retrospective data from patient files			
Center characteristics	X			3
Physician experience and treatment preference	X			
Patient demographics	X		ė.	
Patient socio-demographics	X			X
Medical History and PD History	X			X
PD medication before starting LCIG	X			
Add-on PD medication since LCIG initiation		X	X	X
Clinical PD status	X	X		
LCIG infusion data		X	X	X
Concomitant Medication (for indications secondary to PD)	X	X	X	X
Behaviour/mentation/mood (UPDRS Part I)	X		2	X
Activities of daily living (UPDRS Part II)	X			X
Motor examination (UPDRS Part III)	X			X
Treatment complications (UPDRS Part IV)	X			X
Disease Stage (Modified Hoehn & Yahr stage, UPDRS Part V)	X			X
Non-motor Symptoms Scale (NMSS)				X
Questionnaire for Impulsive-Compulsive Rating Scale (QUIP-RS)			6	X
Mini-Mental State Examination (MMSE)	X			X
Quality of Life (PDQ-8)			ā	X
Parkinson's disease Sleep Scale Version 2 (PDSS-2)				X
Healthcare Resource Utilization Questions (HCRU)				X
Beliefs Medication (BMQ)				X
Adverse Events / Adverse Reactions / Product complaint		X	X	X

In detail the following information was documented:

#### 4.4.1 Site information

For each site information was to be documented in the eDRF comprising type of site, origin of service, average number of PD and APD patients per year, average frequency of visits for APD patients on device aided therapy, number of specialist physicians working with PD patients, support services/functions available at the site, access to invasive treatments.

#### 4.4.2 Physician's profile

The physician was requested to document his/her experience in the treatment of APD patients and in the use of LCIG, including therapeutic specialty/-ies, number of years within the management of PD and APD patients, number of years working at current institution, observance of standard treatment algorithm/established guidelines, overall preference on LCIG as monotherapy vs. LCIG plus add-on PD medication, and years of experience and number of patients with LCIG, DBS (Deep brain stimulation) or CSAI (Continuous subcutaneous apomorphine infusion).

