To assess the generalizability of the data from the patients enrolled, the physician will be asked to document on a separate Case Reporting Form the number of patients who are eligible but refuse to participate in the study. Only age ranges (<30 years, 30-45 years, 45-65 and > 65 years) and reason(s) for not participating will be collected.

The primary endpoint of this PMOS will be the percentages of APD patients on LCIG monotherapy right after LCIG initiation and at 3, 6, 9, and 12, respectively.

The secondary endpoints are:

- Descriptive data from patient's PD medication:
 - For add-on PD medication: percentage of patient on each PD medication (by drugs and class), total daily dose and levodopa equivalent Daily dose (LEDD), posology (number of times per day);
 - For LCIG infusion settings and substantial dose adjustments: total dose per day and specific for each type of dose (morning dose and continuous dose) and number of hours of infusion.

- Tapering process: number of days required for the tapering process, total dose per day and posology for add-on PD medication prior to LCIG initiation, at LCIG initiation (titration) or during ongoing LCIG treatment
- Main reasons for introduction or tapering of add-on PD medication or LCIG substantial dose adjustments
- Latency and duration of treatments data:
 - Number of days or months from LCIG initiation until LCIG is given as a monotherapy and the duration of LCIG monotherapy.
 - Number of days or months from LCIG initiation until the introduction or tapering of each PD medication, or until any LCIG substantial dose adjustments.
- LCIG monotherapy vs LCIG plus add-on PD medication data:
 - Healthcare Resource Utilization, as measured by Healthcare Resource Utilization Questionnaire (HCRU)
 - Patient's, caregiver's, and physician's overall preference on LCIG monotherapy vs. LCIG plus add-on PD medication, percentage of patient's and physician's preference for each of the options
 - Predictors for LCIG as monotherapy vs. LCIG plus add-on PD medication based on the patient's profile, including socio-demographics, clinical status (motor and non-motor symptoms), Levodopa-equivalent dose (LED), PD medication and Quality of Life
 - Predictors for LCIG as monotherapy vs. LCIG plus add-on PD medications based on the physician's profile including experience as measured by number of years on APD patient management, number of years using LCIG therapy, and number of patients on LCIG therapy

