#### 6.2 Physician's profile

- Therapeutic specialty (type)
- Number of years physician has been working at the institution
- Approximate number of PD patients treated per year
- Approximate number of APD patients treated per year
- Approximate number of APD patients treated with LCIG per year
- Use of standard treatment algorithms/established guidelines/definitions of PD treatment (yes, no)
  - If yes: specification (multiple answers)
- Overall treatment preference
- Years of DBS experience
- Number of DBS patients
- Years of CSAI experience
- · Number of CSAI patients

Years of LCIG experience

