Backward elimination with a significance level of 0.05 will be applied to stepwise automatically select relevant predictors. Effect estimates and p-values will be given for each (potential) predictor.

For the second multivariable logistic regression model the following variables will be considered as potential predictors (i.e. independent variables):

Table 7-3: Potential predictors used for regression analysis 2

Variable	Range	Dichotomization/Grouping
Approximate number of APD patients treated per year	numeric	-
Years of LCIG experience	numeric	-
Years of DBS experience	numeric	-
Approximate number of APD patients treated with LCIG per year	numeric	-
Number of years physician has been working at the institution	numeric	-
Average number of PD and APD patients per year at center	numeric	-
Number of specialist physicians working with PD patients at center	Numeric	-
Origin of service at center	National health services, Private health services	National health services vs. Private health services
Average frequency of routine visits for APD patients on device aided therapy at center	< 1x/year, 1x/year, 2x/year, 3x/year, > 3x/year	≤ 1x/year vs. ≥ 2x/year
Country		
GNI	numeric	

Categorical predictors will be dichotomized / grouped as shown in Table 7-3 in order to simplify interpretation.

Backward elimination with a significance level of 0.05 will be applied to stepwise automatically select relevant predictors. Effect estimates and p-values will be given for each (potential) predictor.

For both regression models the Gross National Income (GNI) is defined as follows (source: https://data.worldbank.org/indicator/NY.GNP.PCAP.CD):

Country	GNI
Austria	45.44
Bulgaria	7.76
Canada	42.87
Czech Republic	18.16
Croatia	12.43
Estonia	18.19

Greece	18.09
Hungary	12.87
Ireland	55.29
Israel	37.27
Netherlands	46.18
Romania	9.97
Spain	27.18
Sweden	52.59

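### Physician treatment preference and guideline use belong to the physician's profile but are not candidates in the physician predictor model (SAP Table 7-3)

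*SAP*

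**What the plan says.** SAP 3.2 states the objective as "To identify predictors for achieving long-term monotherapy with LCIG vs. LCIG plus add-on PD medication, based on the patient's profile and the physician's profile". Protocol 8.0 gives the same objective.

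The content of the physician's profile is set out in Protocol 9.2.7.2 and SAP 4.4.2. Besides experience and patient numbers, SAP 4.4.2 lists "observance of standard treatment algorithm/established guidelines, overall preference on LCIG as monotherapy vs. LCIG plus add-on PD medication". SAP 6.2 carries both forward as analysis variables: guideline use as a yes/no item, and "Overall treatment preference".

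The protocol endpoint (Protocol 9.1) describes the physician predictors as "physician's profile including experience as measured by number of years on APD patient management, number of years using LCIG therapy", followed by the number of LCIG patients.

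SAP 7.8 fits a second logistic model (model 2) to 12-month monotherapy, once for each monotherapy definition, with the candidates of Table 7-3 and backward elimination at 0.05. The candidates are physician items such as "Approximate number of APD patients treated with LCIG per year", centre items such as "Number of specialist physicians working with PD patients at center", and Country and GNI. Preference and guideline use are not in Table 7-3, nor in Table 7-2 for the patient model.

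**The concern.** Whether LCIG is given alone is a prescribing decision. Of the items in the profile, the physician's stated preference between monotherapy and combination therapy is the one most directly about that decision, and guideline use is the other item about treatment policy. A predictor analysis meant to draw on the physician's profile, but offering only experience, volume and centre items, leaves that policy part out.

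Two things are at stake. First, the multivariable analysis is silent on whether these two items predict monotherapy. Second, if preference differs between more and less experienced physicians, backward elimination may keep an experience or volume term that partly carries the effect of preference, and a reader of model 2 could not tell.

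**Working it through.** **1. Profile items against model candidates.** Table 7-3 has 11 rows.

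| Group | In Table 7-3 | In SAP 6.2 but not in Table 7-3 |
|---|---|---|
| Physician | APD patients per year; LCIG patients per year; years of LCIG; years of DBS; years at institution (5) | guideline use; overall preference; specialty; PD patients per year; years of CSAI; numbers of DBS and CSAI patients |
| Centre | PD/APD patients per year; specialists; origin of service; visit frequency (4) | not applicable |
| Country level | Country; GNI (2) | not applicable |

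**2. Every other planned use of the two items.**
- Preference: a secondary variable in SAP 6.5 under the comparison of monotherapy with add-on therapy. SAP 7.6 reports it overall and by 12-month monotherapy group, and SAP 7.1 gives 95% confidence intervals for proportions if applicable. Protocol 9.7 foresees intervals for group differences if appropriate. The comparison is descriptive and unadjusted.
- Guideline use: only the description of participating physicians in SAP 7.3, which is not split by monotherapy status.

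**3. Room in the model.** The plan states no figure on this point. Its sample size, used here only as context, reproduces: 1.959964² × 0.25 / 0.05² = 384.15, rounded up to the stated 385, with about 400 to be enrolled.

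Table 7-3 uses 5 + 4 = 9 parameters, plus 13 for the 14 countries listed in SAP 7.8. GNI is fixed by country and adds none, so the total is 22. Two binary items make 24. I take the monotherapy rate as 36% to 40%, the registry figure cited in Protocol 7.0; this is an assumption about the present study. Events are then 400 × 0.36 = 144 to 400 × 0.40 = 160.

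| Country-level term | Events per parameter now | With both items added |
|---|---|---|
| Country | 144/22 = 6.5 to 160/22 = 7.3 | 144/24 = 6.0 to 160/24 = 6.7 |
| GNI in place of Country | 144/10 = 14.4 to 160/10 = 16.0 | 144/12 = 12.0 to 160/12 = 13.3 |

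**4. How far experience could stand in for preference.** All inputs of this step except the sample size are assumptions.
- Experience x is standard normal and has no effect of its own.
- Preference is 1 when ρx + √(1−ρ²)e > 0, with e standard normal, so it is split about 50/50.
- logit P(monotherapy) = −0.49 − ln(OR)/2 + ln(OR) × preference, which gives 38% to 39% monotherapy.
- Patients are independent. The model is fitted to 200,000 draws and the standard error is multiplied by √(200,000/400).
- The chance of p<0.05 is Φ(|b|/se − 1.96) + Φ(−|b|/se − 1.96), where b is the experience coefficient with preference left out.

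| Preference OR | ρ | OR per SD of experience, preference left out | Chance of p<0.05 |
|---|---|---|---|
| 2 | 0 | 1.00 | 5% |
| 2 | 0.2 | 1.06 | 9% |
| 2 | 0.4 | 1.12 | 19% |
| 2 | 0.6 | 1.18 | 37% |
| 3 | 0 | 1.00 | 5% |
| 3 | 0.2 | 1.10 | 15% |
| 3 | 0.4 | 1.19 | 39% |
| 3 | 0.6 | 1.32 | 74% |

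With preference in the model, the experience odds ratio lies between 0.997 and 1.015 in all eight settings. The excess over 5% therefore comes from the correlation alone. The illustration has one experience factor; it does not include Country, the other Table 7-3 rows or the elimination steps, and it does not cover guideline use or centre size.

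**The case against.** **The protocol endpoint speaks of experience.** It names years and patient numbers, and preference has its own separate objective. The omission is compatible with that text, and nothing obliges the SAP to include preference as a predictor. But the endpoint wording is open-ended, and Table 7-3 does not keep to it. The table adds origin of service, visit frequency and GNI, and leaves out years of managing APD, which the endpoint names. The endpoint therefore does not explain why the two policy items were dropped, and the SAP gives no reason.

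**Preference is a difficult covariate.** It is documented for a single-visit study of patients already treated for at least 12 months, although SAP Table 4-1 puts it in the column before LCIG initiation. It may summarise what the physician has already prescribed, or lie on the path from experience to monotherapy; adjusting would then remove part of a real experience effect. This stands. It is why the two versions of model 2 should be shown together, and why the version with preference does not replace the other.

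**Guideline use may not point to monotherapy.** It records the use of any algorithm, guideline or definition, and the documents do not say which way it would act. This also stands: the case for it is only that it is in the profile and otherwise never set against the outcome.

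**Other profile items are missing too, and SAP 7.10 allows extensions.** Both are true. Additions made under 7.10 would, however, be chosen after seeing the data.

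**Conclusion.** The concern holds in a limited form. Two items of the profile named in the objective are not candidates in model 2, so that model cannot show whether they predict monotherapy. An experience or volume term it retains may partly reflect preference.

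The size is conditional. With independent patients and a preference odds ratio of 2 to 3, the chance that a null experience factor reaches p<0.05 is about 9% to 15% at correlation 0.2 and 19% to 39% at 0.4, against 5% at zero correlation. The documents give neither the odds ratio nor the correlation.

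Three stronger readings are not supported.
- A reader might infer that both items are never examined against monotherapy. That is true of guideline use only; preference is compared by group under SAP 6.5 and 7.6.
- A reader might infer a much larger error rate. With 40 physicians of 10 patients each, preference odds ratios of 2 to 4 and correlations of 0.2 to 0.5, simulated rates run from 12% to 71%. The same set-up already gives 8% to 19% at zero correlation, which reflects clustering of patients within physicians and not the omission. The cluster sizes are not in the documents either.
- A reader might infer that an experience effect found without preference is false. If preference results from experience, it is not.

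This is a worthwhile, low-cost improvement to an exploratory analysis. It does not affect the primary endpoint.

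**What to change.** Make these changes in SAP 7.8:
- Add guideline use (yes vs. no) to Table 7-3 as a candidate.
- Report model 2 in two pre-specified versions, without and with overall treatment preference (monotherapy vs. LCIG plus add-on), side by side, for both monotherapy definitions.
- State that preference is recorded at study time, may be a mediator or a consequence of past prescribing, and is interpreted only as an association.

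If either item is to stay out, give the reason.

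The cost is at most two more parameters (events per parameter from 6.5–7.3 to 6.0–6.7 under the assumed monotherapy rate, with Country in the model) and one extra model run per monotherapy definition. The data are already collected.
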